9.1 Definitions

9.1.1 Adverse Event

An adverse event is any untoward medical occurrence in a patient or clinical investigation subject administered a pharmaceutical product and which does not necessarily have to have a causal relationship with this treatment. An adverse event can therefore be any unfavorable and unintended sign, including abnormal laboratory findings, symptoms, or diseases temporally associated with the use of a medicinal product, whether or not considered related to the medicinal product. Worsening of a medical condition for which the efficacy of the study drug is being evaluated will not be considered an adverse event.

9.1.2 Unexpected Adverse Event

An unexpected adverse event is one for which the nature or severity of the event is not consistent with the applicable product information, e.g., the Investigator's Brochure.

9.1.3 Adverse Events of Special Interest

For this protocol the collection of Adverse Events of Special Interest (AESI) will be reported following serious adverse event reporting procedures as described below.

For this protocol, a specific AESI includes notification and collections of hypersensitivity reactions associated with the administration of ferumoxytol and will follow Serious Adverse Event notification procedures. Hypersensitivity reaction reports including anaphylaxis/anaphylactoid reactions should include individual signs and symptoms, time to onset, time to resolution and any intervention or medication given for the treatment thereof.

9.1.4 Serious Adverse Event

A serious adverse event (SAE) is any untoward medical occurrence that at any dose:

- Results in death
- Is life-threatening (an event in which the patient was at risk of death at the time of the event; it does not refer to an event which hypothetically might have caused death if it were more severe)
- Requires in-patient hospitalization or prolongation of existing hospitalization
- Results in persistent or significant disability/incapacity
- Is a congenital anomaly or birth defect
- Other important medical events that may not be immediately life-threatening or result in death or hospitalization but may jeopardize the patient or may require intervention to prevent one of the other outcomes listed above. Examples of such events are intensive treatment in an emergency room for allergic bronchospasm; blood dyscrasias or convulsions that do not result in hospitalization; or development of drug dependency or drug abuse.

The term "severe" is often used to describe the intensity (severity) of an event; the event itself may be of relatively minor medical significance (such as a severe headache). This is not the same as "serious", which is based on patient/event outcome or action criteria usually associated with events that pose a threat to a patient's life or functioning.

Death due to disease progression is not considered an SAE and should not be recorded as such. Death due to disease progression should be recorded on the appropriate form in the electronic data capture system. If the primary cause of death is something other than disease progression, then the death should be reported as an SAE with the primary cause of death as the event term, as death is typically the outcome of the event, not the event itself.

9.2 Documenting Adverse Events

SAE reporting will begin on the date the patient provides informed consent to participate in the study. Treatment-emergent adverse event reporting will begin as of the administration of ferumoxytol. The Investigator should elicit information regarding the occurrence of adverse events through open-ended questioning of the patient, physical examination and review of laboratory results.

All adverse events, whether serious or not, will be recorded in the source documents and the adverse event page of the case report form (except as noted below). All new events, as well as those that worsen in intensity or frequency relative to baseline, which occur after first administration of study drug through 30 days following the last dose of study drug, must be recorded. Adverse events should be followed through resolution, where possible. Adverse events that are ongoing at the time of treatment discontinuation should be followed through the 30 day follow up assessment. However, new adverse events considered by the Investigator to be related to MM-398 or ferumoxytol, must be reported any time the Investigator becomes aware of such an event, even if this occurrence is more than 30 days after the last dose of study drug.

Laboratory, vital signs or ECG abnormalities are to be recorded as Adverse Events only if they are medically relevant: symptomatic, requiring corrective treatment, leading to discontinuation and/or fulfilling a seriousness criterion.

Information to be reported in the description of each adverse event includes:

- A medical diagnosis of the event (if a medical diagnosis cannot be determined, a description of each sign or symptom characterizing the event should be recorded)
- The date of onset of the event
- The date of resolution of the event
- A determination of whether the event is serious or not
- Action taken: none; change in the study drug administration (e.g., temporary interruption in dosing); drug treatment required; non-drug treatment required; hospitalization or prolongation of hospitalization required (complete serious adverse event page); diagnostic procedure performed; patient discontinued from the study (complete Final Visit Section of the case report form)
- Outcome: resolved without sequelae; resolved with sequelae; event resolving; event ongoing; patient died (notify the Sponsor immediately, and complete the Serious Adverse Event page and the Final Visit section of the case report form)

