6.1.6 Dose Reductions Due to Toxicity

The toxicity of each cycle must be recorded prior to the administration of a subsequent cycle and graded according to the NCI CTCAE (Version 4.02). All dose reductions should be based on the worst preceding toxicity.

Dosing may be held for up to 2 weeks from the occurrence to allow for recovery from toxicity related to the study treatment. If the time required for recovery from toxicity is more than 2 weeks, the patient should be discontinued from the study, unless the patient is benefiting from the study treatment, in which case the patient's continuation on study should be discussed between Investigator and Sponsor regarding risks and benefits of continuation.

If a patient's dose is reduced during the study due to toxicity, it should remain reduced for the duration of the study; dose re-escalation to an earlier dose is not permitted. Any patient who has 2 dose reductions and experiences an adverse event that would require a third dose reduction must be discontinued from study treatment.

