6.1.6.1 Hematologic Toxicities

Prior to each MM-398 dosing, patients must have:

- ANC $\geq 1500/\text{mm}^3$
- Platelet count $\geq 100,000/\text{mm}^3$

Treatment should be delayed to allow sufficient time for recovery, and upon recovery, treatment should be administered according to the guidelines in the tables below. If the patient had febrile neutropenia, the ANC must have resolved to $\geq 1500/\text{mm}^3$ and the patient must have recovered from infection.

			Modification	
Worst CTCAE Grade	ANC Levels (cells/mm ³)	Occurrence	MM-398 adjustment in patients receiving 60 mg/m ² (and have not been escalated to 80 mg/m ²)	MM-398 adjustment in patients receiving 80 mg/m ² (if dose escalated from 60 mg/m ²)
Grade 1 or 2	1000-1999	Any	Same as previous dose	Same as previous dose
		First	50 mg/m^2	60 mg/m^2
Grade 3 or 4	<1000	Second	40 mg/m^2	50 mg/m^2
		Third	Discontinue from MM-398	Discontinue from MM-398

 Table 7:
 MM-398 Dose Modifications for Neutrophil Count

		Modification	
Worst CTCAE Grade	Occurrence	MM-398 adjustment in patients receiving 60 mg/m ² (and have not been escalated to 80 mg/m ²)	MM-398 adjustment in patients receiving 80 mg/m ² (if dose escalated from 60 mg/m ²)
Grade 1 or 2	Any	Same as previous dose	Same as previous dose
	First	50 mg/m^2	60 mg/m^2
Grade 3 or 4	Second	40 mg/m^2	50 mg/m^2
	Third	Discontinue from MM-398	Discontinue from MM-398

Table 8: MM-398 Dose Modifications for Other Hematologic Toxicities

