 - In the total counts for each severity classification, an individual patient who experiences two AEs of different preferred term of different severities will be included once in the total for each of the appropriate severities.

Tabular summaries will be presented for each cohort and overall for expansion phase. Summaries will include the number and percentage of patients and classified by primary system organ class and preferred term. The following summaries will be reported for AEs, TEAE regardless of drug relationship, TEAE related to study drug, TEAE grade 3 and above regardless of drug relationship, TEAE grade 3 and above related to study drug, serious AEs (SAEs), AE leading to study drug discontinuation, and AE leading to death:

- Overall summary of adverse events will descriptively summarize all adverse events, treatment-emergent adverse events (TEAE), serious adverse events (SAEs), TEAE related to study drug, TEAE with CTCAE grade 3 and above, TEAE related to study drug with CTCAE grade 3 and above, TEAE leading to death, TEAE related to study drug leading to death, TEAE related to study drug leading to discontinuation, and TEAE related to study drug leading to dose adjustment (interruption or decrease).
- Summary of TEAE by system organ class (SOC) and preferred term (PT) by decreasing frequency.
- Summary of TEAE by CTCAE grade, SOC and PT, by decreasing frequency.

- Summary of TEAE related to study drug by SOC and PT, by decreasing frequency.
- Summary of TEAE by CTCAE grade 3 and above, SOC and PT, by decreasing frequency.
- Summary of TEAE related to study drug by CTCAE grade 3 and above, SOC and PT, by decreasing frequency.
- Summary of TEAE related to study drug leading to dose adjustment (interruption or decreased), discontinuation and death by SOC and PT, by decreasing frequency.
- Summary of TEAE related to study drug leading to discontinuation and death by SOC and PT, by decreasing frequency.
- Summary of SAE by SOC and PT, by decreasing frequency.
- Summary of SAE related to study drug by SOC and PT, by decreasing frequency.

Listings of all AEs/TEAEs/SAEs will be presented by treatment group and sorted by patient id, start time, primary system organ class, preferred term and verbatim text for all adverse events recorded during the study, onset day relative to the first treatment date of AEs, date of Resolution, AEs, SAEs, related to study drug.

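### The SAP table of adverse events leading to dose adjustment will omit untreated, asymptomatic, non-serious blood-count abnormalities that delay or reduce MM-398, because Protocol 9.2 does not make them adverse events

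*Protocol*

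**What the plan says.** **What becomes an AE.** The general definition in Protocol 9.1.1 takes in unfavorable signs "including abnormal laboratory findings". Protocol 9.2 then narrows it. Its instruction to record all AEs carries an exception, and the exception covers laboratory, vital-sign and ECG findings: "abnormalities are to be recorded as Adverse Events only if they are medically relevant: symptomatic, requiring corrective treatment, leading to discontinuation and/or fulfilling" (the sentence ends with seriousness as the fourth ground). Delay, interruption and reduction of MM-398 are not among the four grounds.

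**What changes dosing.** Protocol 6.1.6.1 sets minimum neutrophil and platelet counts before each dose and adds: "Treatment should be delayed to allow sufficient time for recovery". Table 7, "MM-398 Dose Modifications for Neutrophil Count", lowers the dose at the first and second grade 3 or 4 occurrence and stops MM-398 at the third. Table 8 does the same for other hematologic toxicities. Neither table asks for symptoms.

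**What is tabulated.** The overall AE summary in SAP 12.1 includes "TEAE related to study drug leading to dose adjustment (interruption or decrease"), and a by-term table follows. SAP 12.1 also tabulates TEAEs of grade 3 and above. All of these start from AE records. SAP 10 counts patients with delays and reductions by cycle. SAP 12.2 summarizes the shift to the most severe laboratory grade and lists all grade 3+ laboratory results after baseline.

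**The concern.** A reader will take the dose-adjustment table as the account of which drug-related toxicities forced changes to MM-398. For hematologic toxicity that account is incomplete by construction. The blood count that delayed or reduced a dose need not exist as an AE, so it cannot appear in a table built from AEs.

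Safety of MM-398 in the presence of ferumoxytol is a secondary objective in all phases. Neutropenia was the most common grade 3+ event in PEP0208. The NAPOLI-1 hematologic rates in Protocol Table 4 are based on laboratory values, so an AE-based grade 3+ neutropenia rate from this trial would not be comparable with them.

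**Working it through.** This is a check of one rule against another. No figure in the plan is disputed.

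**Step 1. Could 'corrective treatment' cover a dose change?** Not on a natural reading. The action-taken field in Protocol 9.2 lists "change in the study drug administration (e.g., temporary interruption in dosing") as a category apart from drug treatment required, non-drug treatment required and discontinuation. That field is also completed only once an AE has been recorded.

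**Step 2. Follow typical findings through the plan.** Assume no symptoms and no seriousness. Grades are from SAP Appendix A.

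| Finding | Effect under Protocol 6.1.6.1 | AE under 9.2? | SAP 12.1 tables |
|---|---|---|---|
| ANC 1000–1499 before a dose (grade 2), untreated | Delay, same dose | No | Missing from dose-adjustment table |
| Platelets 75,000–99,999 before a dose (grade 1), untreated | Delay, same dose | No | Missing from dose-adjustment table |
| ANC 500–999 (grade 3), untreated, first or second occurrence | Reduction; delay only if not recovered by the dosing day | No | Missing from dose-adjustment and grade 3+ tables |
| ANC below 500 (grade 4), antibiotic given as in Protocol Table 11 | Reduction | Yes, treated | Present |
| Grade 3 or 4 neutropenia given G-CSF | Reduction | Yes, treated | Present |
| Third grade 3 or 4 occurrence | Discontinuation | Yes | Present |

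The third and last rows can belong to one patient. The AE record may then show the discontinuation but not the two episodes that reduced the dose before it.

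**Step 3. Does another planned output make the link?**

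- SAP 10 gives numbers of patients with delays and reductions, without cause.
- SAP 12.2 gives laboratory grades, without dosing.
- Protocol 6.1.6 requires that "The toxicity of each cycle must be recorded prior to the administration of a subsequent cycle", with a CTCAE grade, but does not say that this goes on the AE page. It does not displace the restriction in 9.2.

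So the ingredients exist in separate outputs, and no planned table joins them.

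**Step 4. Can the number be sized?** The documents give three earlier grade 3+ neutropenia rates: 12/40 = 30% (PEP0208, reported as an AE rate), 16% (NAPOLI-1 monotherapy, laboratory) and 20% (NAPOLI-1 combination, laboratory). Applied to about 30 Expansion Phase patients:

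- 30 × 0.16 = 4.8
- 30 × 0.20 = 6.0
- 30 × 0.30 = 9.0

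The share meeting no ground in 9.2 is not in the documents. If it is assumed to lie between 25% and 75%, the product runs from 4.8 × 0.25 = 1.2 to 9.0 × 0.75 = 6.75 patients. This shows only how far the answer depends on the assumption:

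- The source rates come from pancreatic cancer, at 120 mg/m² every three weeks or at 80 mg/m² every two weeks with 5-FU/LV. Here MM-398 is given alone every two weeks, from 60 mg/m² in the current protocol, and the Expansion Phase is in breast cancer.
- The protocol itself says that the PEP0208 neutropenia was possibly related to earlier gemcitabine.
- The two ends multiply low by low and high by high.
- The calculation leaves out the delay-only findings in the first two rows of the table, so the top of the range is not a ceiling either.

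**The case against.** **Most severe episodes are already captured.** Where Protocol Table 11 is followed, an ANC below 500 calls for an oral antibiotic whether or not there is fever, which makes it an AE. G-CSF use, a third occurrence and a judgment of seriousness also qualify; Protocol 9.1.4 names blood dyscrasias among possible important medical events. This stands. A reader might infer that all asymptomatic grade 3 or 4 neutropenia escapes, but the documents do not support that. What remains is mainly untreated, non-serious grade 3. Some grade 4 could remain where a site follows its own guideline, which Protocol 6.4.3 allows.

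**Grade 3+ neutropenia is reported.** SAP 12.2 has the shift table and the listing, and keeping laboratory-only events out of AE tables is a common convention. This also stands. It answers the grade 3+ table almost fully, provided that the table states the exclusion. It does not answer the dose-adjustment table, because SAP 12.2 carries no dosing information.

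**The starting-dose change.** A reader might infer that the gap weakens the evidence behind the lower starting dose. It does not. The summary of changes to version 5 gives gastrointestinal events as the reason. These are largely symptomatic clinical events, outside the laboratory restriction.

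**Delay and reduction follow different rules.** Delay depends on the pre-dose count; Tables 7 and 8 govern reduction. A grade 3 nadir that has recovered by the dosing day need not delay anything.

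**Unseen material.** The CRFs and mock shells cited in the SAP are not available here. They may record a reason for each dose change. That would make the fix easier, but the SAP text plans no table from it.

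**Conclusion.** The point holds in a limited form. Followed as written, the plan gives a dose-adjustment table that omits untreated, asymptomatic, non-serious hematologic abnormalities that delayed or reduced MM-398. Its grade 3+ TEAE table omits those of grade 3 or higher. The laboratory data are not lost; what is missing is the link to dosing.

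The conclusion rests on two readings: that the list in Protocol 9.2 is closed, and that a dose change is not itself corrective treatment. Sites reading 9.2 more loosely would record some of these events, which would narrow the gap but make capture uneven.

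The size is unknown. A reader might take one to seven missing patients from the arithmetic above, but that range depends on an assumed share and borrowed rates and should not be quoted as an estimate. In a descriptive phase 1 study whose primary objectives are imaging and tumor drug levels, this is a modest reporting defect. It is worth correcting because the correction is cheap.

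**What to change.** **Main change, in the SAP only.** Add to SAP 12.1 a derived count of patients with a hematologic laboratory abnormality, by CTCAE grade, followed by an MM-398 delay or reduction. Show it beside the TEAE dose-adjustment table. Build it from the laboratory and dosing data already collected, and apply it in the same way to every patient.

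Two definitions need fixing beforehand:

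- The laboratory window, for example results after the preceding dose and up to the affected one.
- What counts as a delay. SAP 10 does not define it; a dose given later than the ±2-day allowance in Protocol 6.1.3 would serve.

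Label the result as dose changes preceded by the abnormality, since another toxicity may have contributed. Add a footnote to the AE tables that laboratory-only events are excluded under Protocol 9.2.

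**Optional change, in the protocol.** Reconcile 9.2 with 6.1.6 by adding dose delay, interruption or reduction as a recording ground for future patients. By the version 5 safety review, 16 Expansion Phase patients were already enrolled, so this would put two capture rules into a group of about 30. The report would have to say so, and the derived table would still be needed.

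**Cost.** One extra derived table, one footnote and a slightly less favorable tolerability summary. The optional change adds some AE entries at sites. No dosing rule is affected.

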9.3 Reporting Serious Adverse Events

All fatal or life-threatening adverse events or adverse event of special interest (AESI) must be reported to the medical monitor immediately by telephone or e-mail. Within 24 hours of knowledge of the event, the Serious Adverse Event Form must be faxed to the appropriate contact whether full information regarding the event is known or not. Additional follow-up by the Investigator will be required if complete information is not known. Source documentation of

all examinations, diagnostic procedures, etc., which were completed with respect to the event should be included with the SAE form. Care should be taken to ensure that the patient's identity is protected and the patient's identifiers (as assigned at the time of study enrollment) are properly mentioned on any copy of source document provided to the Sponsor. For laboratory results, include the laboratory normal ranges.

In case of accidental or intentional overdose of MM-398, even if asymptomatic or not fulfilling a seriousness criterion, the overdose is to be reported to the Sponsor immediately (within 1 working day) using the AE and SAE forms. Overdose of MM-398 will be defined as \geq 133% of planned dose.

All other serious adverse events must be reported to the appropriate contact within 24 hours of becoming aware of the event by phone, e-mail or fax. The Serious Adverse Event Form must also be faxed to the appropriate contact within 24 hours of the event whether full information regarding the event is known or not. Additional follow-up by the Investigator will be required if complete information is not known.

The medical monitor shall be contacted as deemed necessary by the site. Current contact information shall be maintained at the site within the regulatory binder.

All SAEs will be evaluated by the medical monitor. If meeting the requirements for expedited reporting, the Sponsor will report the adverse event to all regulatory authorities with jurisdiction over ongoing trials with the study drug and to all other Investigators involved in clinical trials with the study drug. The Investigator is responsible for reporting all SAEs to the appropriate Institutional Review Board (IRB).

9.4 Determining the Severity and Relatedness of Adverse Events

9.4.1 Grading the Severity of an Adverse Event

Each adverse event will be graded according to the NCI CTCAE Version 4.02, which may be found at http://ctep.cancer.gov/reporting/ctc.html. For events not listed in the CTCAE, severity will be designated as mild, moderate, severe or life threatening or fatal which correspond to Grades 1, 2, 3, 4 and 5, respectively on the NCI CTCAE, with the following definitions:

- **Mild**: an event not resulting in disability or incapacity and which resolves without intervention;
- **Moderate**: an event not resulting in disability or incapacity but which requires intervention;
- Severe: an event resulting in temporary disability or incapacity and which requires intervention;
- Life-threatening: an event in which the patient was at risk of death at the time of the event
- Fatal: an event that results in the death of the patient

9.4.2 Relatedness to Study Drug

The Investigator must attempt to determine if there exists reasonable possibility that an adverse event is related to the use of the study drug, according to the following guidelines:

The Investigator must attempt to determine if an adverse event is in some way related to the use of the study drug. This relationship should be described as follows:

- Unlikely: The event is clearly due to causes distinct from the use of the study drug, such as a documented pre-existing condition, the effect of a concomitant medication a new condition which, based on the pathophysiology of the condition, and the pharmacology of the study drug, would be unlikely related to the use of the study drug
- **Possible**: The event follows a reasonable temporal sequence from administration of the study drug and the event follows a known response pattern to the study drug BUT the event could have been produced by an intercurrent medical condition which, based on the pathophysiology of the condition, and the pharmacology of the study drug, would be unlikely related to the use of the study drug or the event could be the effect of a concomitant medication
- **Probable**: The event follows a reasonable temporal sequence from administration of the study drug and the event follows a known response pattern to the study drug AND the event cannot have been reasonably explained by an intercurrent medical condition which or the event cannot be the effect of a concomitant medication
- **Definite**: The event follows a reasonable temporal sequence from administration of the study drug, the event follows a known response pattern to the study drug and based on the known pharmacology of the study drug, the event is clearly related to the effect of the study drug
- Unknown: Based on the evidence available, causality cannot be ascribed

